#### 4.3.4 Drug records

The Investigator or a designated person must keep records of all the drugs in the center during the study by means of completing record forms for the drugs provided by the Sponsor. Records of investigational drugs will be controlled by the Monitor regularly.

The Investigator or any designated person will count the number of packages of used or unused drugs returned by the patient and enter this data into the record forms for the drugs in CRFs. Moreover, CRFs will contain the number of missing visits, investigational product dose changes (if any, according to the patient diary).

#### 4.3.5 Return and destruction of drugs

Upon completion of the study or in case of early study termination on the part of the study site, all unused investigational products and packages of used preparations must be returned to the Sponsor. The Sponsor is responsible for the destruction of investigational products. After the counting of all the packages of used and unused drugs and control of the packaging labels, the Monitor organizes drug shipping to the Sponsor for the following destruction.

## 4.4 Subjectivity minimization measures

#### 4.4.1 Randomization

A randomized open prospective comparative phase III trial in parallel groups with active control is planned.

Randomization is a measure aimed at minimizing subjectivity due to the random distribution of the patient. Randomization will exclude the subjective, including unconscious, selection by the researcher in one of the patient population groups, which will differ significantly from the population recruited in the second.

Automated randomization lists will be formed, randomization will be carried out through the e-CRF system with a randomization module.

Each randomized patient will be assigned a unique number for issuing the drug during the study. The patient's number consists of the letter R and the numbers from 001 to 336. The numbering of patients does not depend on the research center and is "transparent". In addition to the number, the system will indicate the treatment group to which the patient is distributed. Randomization will be stratified by two factors depends on patient's data (gender and baseline Hb level) entered to the e-CRF before randomization:

- Gender (male vs female);

- Hb level (80–94 g/L vs 95–110 g/L).

In order to randomize patients in the e-CRF system, each center will be provided with secure access and appropriate training in the use of the system will be provided.

The randomization number and name of the treatment group issued by the system. The researcher records in the primary documentation and enters information on the randomized patient in the list of included patients. The randomization number cannot be changed during the study.

The drug is given to the patient according to the information on the group of therapy received from e-CRF system. Research therapies also cannot be changed during the research process.

### 4.4.2 Blinding

The study treatment is prescribed openly. Blinding within this study is not planned.

### 4.5 Dosing schedule for investigational products

Study product Ferrum Lek® (iron-III-hydroxide polymaltosate), 100 mg chewable tablets (Lek d.d., Slovenia), 2 tablets daily (200 mg), during or right after meals; the daily dose should be administered once daily.

Reference product MALTOFER® (Vifor S.A., Switzerland) (iron-III-hydroxide polymaltosate), chewable tablets, 2 tablets daily (200 mg), during or right after meals; the daily dose should be administered once daily.

## 4.6 Dosage form, package and labeling of the investigational products

#### 4.6.1 Dosage form

**Investigational products:** Ferrum Lek®, 100 mg chewable tablets (Lek d.d., Slovenia). Dark brown round flat tablets with light brown impregnations and a bevel.

**Reference product:** MALTOFER® (Vifor S.A., Switzerland) 100 mg chewable tablets. Dark brown, round, flat scored tablets with white impregnations.

#### 4.6.2 Container

**Investigational products:** 100 mg chewable tablets. 10 tablets per strip or blister. 3, 5 or 9 strips or blisters in a carton pack along with the Patient Information Leaflet.

**Reference product:** 100 mg chewable tablets. 10 tablets in polyethylene laminated aluminum foil blisters. 1 or 3 blisters per carton pack along with the Patient Information Leaflet.

#### 4.6.3 Labeling of the study drugs

This study is open-label, the study site will be provided with the packed drug products from the series commercially available.

Each package, in addition to the commercial label with the name, composition, shelf life and drug product manufacturer, will be labeled with a sticker containing following information: note "For Clinical Trials Only", clinical study protocol number, name and contacts of the study Sponsor and Investigational Site, and place for writing patient' randomization number.

The label should not cover the drug name, active substances, and their strength, shelf life, manufacturer name.

## 4.7 Duration of patients participation in the study

Duration of each patient participation in the study will be not longer than 98 days (including screening, 7 days; randomization and treatment,  $84 \pm 2$  days).

Minimal duration of patients participation in the study: 83 days (on condition of minimally acceptable treatment duration and screening duration, 1 day).

## 4.8 Rules of termination of clinical study parts or the study on the whole

The study may be terminated on the following grounds:

- 1. Upon the Sponsor's initiative:
  - a. availability of new toxicological or pharmacological data, or data on SAE which require re-consideration of the previous evaluation of the benefit/risk ratio.
  - b. AEs incidence or severity require the study termination;
  - c. other reasons including administrative ones.
- 2. Upon the Investigator's initiative: AEs incidence or severity unacceptably increases risk of patients participation in the study.
- 3. Upon the decision of the regulatory authorities.

In the case of early termination of the study, the Sponsor must inform the study site personnel as well as regulatory authorities with indication of the reason thereof.

## 4.9 Record keeping procedures for investigational drug products

The study sites will be provided with the investigational product (the study product and reference product) in the amounts sufficient for the study completion, taking into account the planned number of patients to be screened.

An authorized study site specialist shall keep a logbook for the drugs where the drugs delivery to the study site, dispensing to the subjects, and return of the unused drugs are noted. Storage conditions must be also noted. The study drugs may be used for the purposes of this clinical study only.

Authorized representatives of the Sponsor or regulatory authorities may check the drugs log or availability of the drugs at stock during the study site audit/monitoring. The drugs must be stored under the required conditions in a room with an access for the authorized personnel responsible for the drugs dispensing only.

## 4.10 Storing and unblinding of randomization codes

The table with treatment randomization codes will be stored in Sponsor's company, the access to this information will be restricted to designated persons. Procedures of unblinding of randomization codes are not applicable within this study, as the blinding of treatment groups for this study is not planned.

Randomization plan will be known to the investigating physician, the Principal Investigator, the Sponsor, the regulatory authorities (in observation of serious adverse events).

# 4.11 List of data registered in Case Report Form (without preliminary written or electronic record) and recognized as primary data

All study data will be entered into primary documentation and CRFs.

## 5 Selection and exclusion of patients

## 5.1 Inclusion criteria

Patients will be included into the study, if they comply with the following criteria:

- 1) The signed and dated written informed consent prior to participation in the study.
- 2) Men and women aged 18 and older (by the time of screening).
- 3) Outpatients.
- 4) Diagnosed iron-deficiency anemia, based on two criteria:
  - a) hemoglobin level below 110 g/L (in men and women), but above 80 g/L,
  - b) serum ferritin levels below 30  $\mu$ g/L.
- 5) Women are eligible for enrollment if they are:

a) **not fertile** (i.e., women in postmenopause or after surgical sterilization). Surgically sterile women are considered as female subjects with documented hysterectomy and/or bilateral ovariectomy and/or tubal ligation. Women in postmenopause are considered as women with menostasia for more than 1 year, with the corresponding clinical profile, e.g. older than 45 years, in absence of hormonal replacement therapy. However, in case of doubt, a blood sample shall be taken, where FSH content shall be above 40 IU/ml, and estradiol content – below 40 pg/ml (below 140 pmol/L), in order to confirm postmenopause.

#### OR

b) **fertile**, but the result of pregnancy test at screening is negative, and the subject agrees to use one of the following contraception methods constantly and properly (i.e. in accordance with the approved prescribing information and the doctor's orders) during the whole period of participation in the study:

i) Total sexual abstinence

ii) Oral contraceptives (combination drugs containing progestogen, or progestogen alone)

- iii) Injectable progestogen
- iv) Levonorgestrel implants
- v) Estrogen-containing vaginal ring
- vi) Transdermal contraceptive patches
- vii) Intrauterine device or intrauterine system

viii) A male partner has been sterile (vasectomy with documented azoospermia) **prior to enrollment of a woman**, provided that he is the only partner of the female subject. For the purpose of this definition, "documented" is related to the result of a subject's medical examination by an investigator/responsible person or a subject's past medical history review for assessment of eligibility for enrollment, obtained during the interview with a subject or from his/her medical records.

ix) Double barrier method: a condom or an occlusive cap (diaphragm or cervical/vault caps) with a spermicide (foam/gel/film/cream/suppository).

### 5.2 Non-inclusion criteria

Patients cannot take part in the study if they comply with any of the following criteria:

- 1) Administration of any iron-containing drugs during the last 3 months.
- 2) History of erythropoietin drugs administration.

3) Hypersensitivity to iron therapy (both Oral and/or IV administration) and other components of the study drugs.

4) Hormone therapy (including the use of androgens/anabolic steroids) or administration of drugs that inhibit blood formation, less than 3 months before the start of the study.

5) History of severe allergic reactions or drug intolerance.

6) Fructose intolerance, glucose-galactose malabsorption syndrome, and sucrase-isomaltase deficiency.

- 7) Pregnant or lactating women, or women intending to become pregnant during the study.
- 8) Failure of iron therapy for iron-deficiency anaemia in a subject's past medical history.
- 9) Heme metabolism disorders (e.g., sideroachrestic anaemia, lead anaemia, thalassaemia).
- 10) Iron overload including haemochromatosis and hemosiderosis
- 11) Other causes of anemia, apart from iron deficiency, including:
  - a) Haemolysis (determined as per analyses results at screening, or as per anamnestic data),
  - b) Vitamin B12 and folic acid deficiency (as per the screening data),
  - c) Chronic kidney disease (creatinine clearance at screening is below 90 ml/min (based on Cockcroft-Gault Formula)),
  - d) Systemic connective tissue diseases, chronic infectious diseases requiring regular therapy (as per the past medical history), and other conditions which may, in the investigator's opinion, be accompanied by anaemia of chronic diseases.
- 12) Dysfunction of the thyroid gland (based on the data obtained at screening).
- 13) Laboratory and clinical signs of an active inflammatory process for 10 days before screening.
- 14) AST, ALT, and total bilirubin levels exceeding the upper limit of normal 1.5 times and more.
- 15) Clinically apparent hypothyroidism, in the investigator's opinion.
- 16) Malignant diseases, including blood and lymphoid tissue disorders (leukemia, Hodgkin disease, myelodysplastic syndrome, myeloma, etc.) at screening or in the past medical history, provided that the remission was less than 5 years before screening.
- 17) Signs of bone marrow aplasia at screening or history of bone marrow aplasia.
- 18) The necessity of parenteral iron therapy, i.e. the following cases:
  - a) impaired absorption in case of an intestinal pathology (enteritis, coeliac disease, malabsorption, small intestinal resection, stomach resection, including the duodenum);
  - b) exacerbation of gastric or duodenal ulcer;
  - c) the necessity of quick iron saturation, e.g. in patients with iron-deficiency anaemia with upcoming surgery;
  - d) continuous vast blood loss and other causes, at the discretion of the investigator.
- 19) Known presence of an active infection caused by Helicobacter pylori. In case of presence of Helicobacter pylori, a subject may be enrolled after eradicative therapy.
- 20) Concomitant diseases and conditions, which, in the investigator's opinion, pose risk to a subject's safety in case of his/her participation in the study, or able to affect the safety data analysis in case of exacerbation of this disease/condition during the study, including:
  - a) Myocardial infarction or stroke within 6 months before screening.
  - b) Unstable angina;
  - c) Severe arrhythmia, not controlled by drug therapy;
  - d) Decompensated diabetes mellitus;
  - e) Nephrological disorders;
  - f) Other significant diseases, at the discretion of the investigator.
- 21) HIV infection (as per the screening data or the results of analysis performed within 6 months before screening).
- 22) Known or suspected drug or alcohol abuse for the last 2 years.
- 23) Suspected poor adherence of a subject (e.g., due to mental disorders).
- 24) Participation in any clinical drug studies less than 3 months before the study.
- 25) Blood donation/blood transfusion within 30 days prior to screening or planned blood transfusion at time of screening.

26) History of smoking, unless leave off smoking > 6 months.

)

## 5.3 Exclusion criteria

#### 5.3.1 Terms and conditions for the subjects exclusion from the study

The subjects may be excluded from the study on their own free will at any moment, without giving any reason, as well as upon decision of the Investigator or Sponsor in cases when continuation of the participation may inflict harm to the patient's health and/or life. In addition, the patient must be excluded in the cases listed below:

- 1. Negative trend of the disease
- 2. The Ethics Committee, regulatory authorities or Sponsor terminate the study or participation of the specific study site for any reason.
- 3. The Investigator's decision to withdraw the patient from the study in the interests of the patient.
- 4. Withdrawal of the informed consent (unwillingness of the patient to continue his/her participation in the study).
- 5. Serious deviation from the study protocol;
- 6. Individual intolerance of study drugs;
- 7. Clinically significant adverse event or serious adverse event related to investigational drug;
- 8. Patient's non-compliance;
- 9. False inclusion (e.g., the patient was included in breach of the inclusion/non-inclusion criteria);
- 10. The patient complies with the non-inclusion criteria during the study;
- 11. Patient receives/needs additional treatment, which may influence the study results or patient's safety;
- 12. Other conditions or events which, in the Investigator's opinion, require the patient's exclusion from the study.

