#### 5.3.1.1 Terms and volume of data on the excluded subjects

In the case of study discontinuation on the subject's free will, the Investigator should make effort to find out the reason thereof. In the case of study discontinuation due to AEs/SAEs, the subject should be followed-up until the AEs/SAEs are resolved. In case of early study termination by a patient, he/she should visit the study site for early termination procedures (as an unscheduled visit); if the patient refuses to visit the study site, he/she should be contacted by phone with further recording of all available information.

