## 5.3.2 Terms and conditions for suspension or discontinuation of the study therapy

The patients may stop taking the study drugs according to the protocol or upon withdrawal from the study.

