#### **5.3.3** Replacement of the excluded subjects

Replacement of the excluded patients during the study is not provided for.

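### Section 5.3.1 removes patients from the study, not only from the drug, for reasons that can track poor response, and no Week 12 haemoglobin is then provided for; if the test product is truly worse, this risks favouring non-inferiority.

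*Protocol*

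**What the plan says.** Protocol 5.3.1, on exclusion from the study, moves from voluntary withdrawal to an obligation: "In addition, the patient must be excluded in the cases listed below". The list includes "Negative trend of the disease" (item 1), "Individual intolerance of study drugs" (item 6), a clinically significant or serious related adverse event (item 7), "Patient's non-compliance" (item 8) and "Patient receives/needs additional treatment, which may influence the study results or patient's safety" (item 11). Item 1 carries no haemoglobin criterion and no timing.

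For early termination by a patient, 5.3.1.1 states that "he/she should visit the study site for early termination procedures (as an unscheduled visit"), or is telephoned on refusing to attend. The procedures of that visit are not listed, and Table 5 has no column for it. Patients who leave because of adverse events are followed until the event resolves, with no mention of haemoglobin.

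Section 5.3.2 is a single sentence: "The patients may stop taking the study drugs according to the protocol or upon withdrawal from the study". Section 5.3.3 adds: "Replacement of the excluded patients during the study is not provided for".

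On the analysis side:
- Haemoglobin is scheduled at screening and Weeks 4, 8 and 12 (Protocol 7.1).
- The ITT set needs haemoglobin before and after treatment (Protocol 9.8), or one efficacy visit (SAP 4.3.2).
- Protocol 9.6 and SAP 3.2 plan maximum likelihood for missing primary endpoint data, if needed, without stating a model.
- The primary ANCOVA (SAP 8.1) has no Week 4 or Week 8 haemoglobin term.

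**The concern.** The trial is open-label (Protocol 4.4.2), and blood counts are taken at Weeks 4 and 8. An investigator applying item 1 may therefore be acting on earlier values of the primary endpoint variable. Item 11 may also follow poor response. Intolerance and non-compliance are not poor response in themselves, but they can go with it.

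If the test product is worse, more of its patients meet these conditions, and those who remain look more alike across arms than the randomized groups would. In a non-inferiority trial that favours the sponsor's hypothesis. The per-protocol set holds only patients who escaped the rules, so it is not an independent check. The ITT set holds removed patients only with an earlier value, an off-schedule value or a filled-in one. A Week 12 sample that was never drawn cannot be obtained later.

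**Working it through.** **1. The plan's own figure.** Inputs from Protocol 9.3: margin 5 g/L, SD 15 g/L, true difference 0, power 80%, final critical value 1.976, 15% withdrawal.

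n per group = 2 × [15 × (1.976 + 0.8416) / 5]² = 142.9, so 143, as stated. 143 / 0.85 = 168.2, against the plan's 168. The sample size is not in dispute. The reference rate for false non-inferiority is one-sided 2.5%.

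**2. Removal on observed haemoglobin.** From the plan: SD 15 at Week 12, 168 per arm, critical value 1.976, and a control rise of 11.5 g/L (midpoint of its 8–15 g/L range). Assumed: test rise 6.5 g/L, so the true deficit equals the margin; means rising linearly; SDs of change 9 and 12.5 g/L at Weeks 4 and 8; a patient is removed if haemoglobin has fallen more than 10 g/L at either visit. There were 4,000 simulated trials per row, analysing completers only.

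| Adjacent-visit correlation | Observed deficit (g/L) | False non-inferiority |
|---|---|---|
| 0.5 | 4.32 | 5.7% |
| 0.7 | 4.17 | 7.8% |
| 0.85 | 3.99 | 8.4% |

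Removal was 10–12% in control and 15–18% in test. With everyone retained, the rate was 2.1–2.9%. A 5 g/L trigger gave about 7–13% and a 15 g/L trigger about 4–6%. A repeat run at the 10 g/L trigger gave 4.6–8.7%. A likelihood estimate using Week 4 and 8 haemoglobin returned a deficit of 5.0 g/L and 2.2–2.7% across all these triggers and correlations.

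**3. Other removal mechanisms.** Separate assumptions: control rise 12 g/L, true deficit 5 g/L, correlation 0.75 between adjacent visits and 0.6 between Weeks 4 and 12, 15% removed overall, 3,000 trials per row.

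| Who is removed | Completers: deficit; false NI | Likelihood with Weeks 4/8: deficit; false NI |
|---|---|---|
| Nobody | 5.0; 2.2% | 5.0; 2.2% |
| Random 15% | 5.0; 2.3% | 5.0; 2.3% |
| Lowest Week 8 change | 3.8; 11.4% | 5.0; 2.8% |
| Lowest Week 12 change (unseen) | 3.3; 23.4% | 3.9; 10.4% |

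Over 5–15% removal, completers-only analysis gave 5.7–23.4%. Likelihood gave 2.3–2.8% when removal followed Week 8 haemoglobin and 5.2–10.4% when it followed the unseen Week 12 value.

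**4. No true difference.** With equal arms and the same removal rule in both, the mean estimate was about 0.0 under every mechanism.

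**5. Using Week 12 values after other treatment.** In the step 2 setting, if removed patients in both arms are treated otherwise and reach about +11.5 g/L (an assumed value), entering those values as observed gives about 13–18% false non-inferiority.

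**The case against.** The strongest reply is that the plan already contains the remedy. Haemoglobin is measured at Weeks 4 and 8, ITT is the stated analysis population, and maximum likelihood is planned for the primary endpoint. If removal depends only on recorded haemoglobin, the data are missing at random, and step 2 shows that a likelihood estimate restores the right answer. A reader might infer that no later method can repair the loss; the documents do not support that.

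Nor do they support the inference that the comparison is biased towards non-inferiority as it stands. That needs a true deficit or unequal removal, together with an analysis that fails to recover the missing values. Unequal discretionary removal in an open-label trial could push either way.

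The text is also less absolute than it may seem. Section 5.3.2 can be read as allowing drug to stop without study exit. Section 8.3.4 lists interruption and permanent discontinuation of the product as actions for an adverse event. No passage forbids a Week 12 sample.

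What remains: the likelihood model is unstated and applies only if needed. Patients removed before Week 4 have no scheduled post-baseline haemoglobin. Removal for intolerance, non-compliance or at discretion need not follow recorded haemoglobin. The sensitivity analysis in Protocol 9.6 concerns uncorrectable data errors, not informative dropout.

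**Conclusion.** The point holds as a risk. Study exit is compulsory for reasons that can be linked to response or tolerability, and nothing provides for Week 12 haemoglobin afterwards from patients who still consent. At a true 5 g/L deficit and a 10 g/L trigger, a completers-type analysis gives about 6–9% false non-inferiority instead of 2.5%, with the low-correlation end nearer 5% in a repeat run. A likelihood analysis using Weeks 4 and 8 brings this to about 2–3% if removal follows recorded haemoglobin, but leaves 5.2–10.4% if it follows unseen response.

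The triggers, visit SDs, correlations and removal mechanisms are assumptions; the protocol gives no threshold for item 1. Removal for intolerance, adverse events and non-compliance was not modelled separately. The figures show direction and plausible size. They do not forecast this trial.

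**What to change.** **Protocol.** Reconcile 5.3.1, 5.3.1.1 and 5.3.2 with 8.3.4, and with the study exit for pregnancy in 8.3.6, so that stopping study drug and leaving the study are distinct events. This need not change any clinical decision to stop. Ask patients taken off drug who still consent and can safely continue to attend the remaining scheduled visits, including the Day 84±2 central-laboratory blood count, and record any other iron, transfusion or other treatment. Include a blood count in the early termination visit and say whether that visit covers exclusions the protocol imposes.

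**SAP.** State that the likelihood model uses Week 4 and 8 haemoglobin. Prespecify how Week 12 values after other anaemia treatment enter the primary analysis; they should not enter automatically as observed, because of step 5. Add a sensitivity analysis for informative missingness, such as a delta-adjusted or tipping-point analysis.

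**Cost.** A protocol amendment, up to about 50 patients (0.15 × 336 = 50.4) attending visits already scheduled, and some Week 12 values measured after other treatment.
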